Patients randomised to Regimen B after Version 10.0 has been implemented will be treated with amikacin instead of kanamycin in all sites in which the national TB program is using amikacin for patients requiring an injectable agent, and amikacin is available for the trial. Kanamycin will continue to be used until the transition to amikacin takes place within each country programme.

Patients should be treated with the fluoroquinolone and injectable allocated at randomisation unless there is a clinical or operational reason to make a change.

**Table 2: Regimen Blev doses** (for patients randomised under Version 8.0 of the protocol onwards)

Product	Weight group					
Froudet	Less than 33 kg	33 kg to 50 kg	More than 50 kg			
Levofloxacin	750 mg	750 mg	1000 mg			
Clofazimine	50 mg	100 mg	100 mg			
Ethambutol	800 mg	800 mg	1200 mg			
Pyrazinamide	1000 mg	1500 mg	2000 mg			
Isoniazid	300 mg	400 mg	600 mg			
Prothionamide	250 mg	500 mg	750 mg			
Kanamycin/amikacin*	15 mg per kilogram body weight (maximum 1g)					

\*With Version 10.0 amikacin or kanamycin may be used

The investigative regimens for the Stage 2 comparisons are Regimen C and Regimen D.

Regimen C is an all-oral regimen that is a modification of Regimen B, and consists of bedaquiline, clofazimine, ethambutol, levofloxacin, and pyrazinamide given for 40 weeks, supplemented by isoniazid and prothionamide in the first 16 weeks (intensive phase). All drugs are given daily (seven days a week), except for bedaquiline which is given daily for the first two weeks and then thrice-weekly from Week 2 onwards. The intensive phase should be extended from 16 to 20 or 24 weeks for patients whose smear has not converted by 16 or 20 weeks, respectively, as described in section 7.3.2. If the intensive phase is extended beyond 16 weeks, then the overall treatment time will be extended except for bedaquiline, which will not be given for longer than 40 weeks in total.

Table 3: Regimen C doses, given daily unless otherwise stated

Product	Weight group					
Troduce	Less than 33 kg	33 kg to 50 kg	More than 50 kg			
Bedaquiline	400 mg once dail	y for first 14 days/200 thereafter	0 mg thrice weekly			
Levofloxacin	750 mg	750mg	1000 mg			
Clofazimine	50 mg	100 mg	100 mg			
Ethambutol	800 mg	800 mg	1200 mg			
Pyrazinamide	1000 mg	1500 mg	2000 mg			
Isoniazid	300 mg	400 mg	600 mg			
Prothionamide	250 mg	500 mg	750 mg			

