Secondary efficacy analyses will be based on data from all visits occurring on or before the projected Week 96 visit of the last patient randomised i.e. approximately end of November 2021. A participant's scheduled last efficacy visit will be their latest scheduled trial visit on or before this date.

For purposes of analysis of the secondary efficacy outcome measures at Week 132 in Stage 2, a patient's outcome will be classified as **favourable** if their last two sputum culture results are

\* Excluding changes from kanamycin to amikacin

negative, unless they have previously been classified as unfavourable. These two sputum results must be from samples taken at separate visits; the latest must be no more than six weeks before their scheduled last efficacy visit.

The visit window for the scheduled last efficacy visit is defined as no more than six weeks prior to and up to six weeks after (or on 30 Nov 2021 if this is earlier) the scheduled last efficacy visit. The end dates of the window will be extended for any Stage 2 patients whose scheduled last efficacy visit was due during the COVID-19 pandemic and did not occur due to restrictions on movement, unacceptable risk of exposure to COVID-19 in connection with the scheduled visit, or any other reason related to the pandemic. For such patients, sputum samples must be taken in a window between six weeks prior to and twelve weeks after the last scheduled visit date (or on 30 Nov 2021 if this is earlier).

A patient's outcome at their scheduled last efficacy visit will be classified as unfavourable if:

- They are unfavourable at Week 76
- They start any MDR-TB treatment between their Week 76 and scheduled last efficacy visits
- They die between their Week 76 and scheduled last efficacy visits
- At least one of their last two culture results, from specimens taken on separate occasions, is positive.

A patient who does not have a culture result within the window for their scheduled last efficacy visit, having not otherwise been classified as unfavourable, will be regarded as **not assessable** and excluded from the analysis provided their last two cultures, from specimens taken on separate occasions, are negative.

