This document describes and substantiates the statistical principles and methods used for the analysis of data from Stage 2 of the STREAM trial. This document is designed to support the STREAM protocol but this Statistical Analysis Plan (SAP) supersedes the SAP as written in the protocol. Every care was taken in the drafting of this SAP, but corrections or amendments may be necessary. A pre-final version (v1.0) of this SAP was signed off before first patient first visit. The final version of the SAP will be signed off before database lock for the primary Week 76 Stage 2 analysis.

The STREAM trial consists of two stages. Stage 1 involves the comparison of two treatment regimens: Regimen A and Regimen B. Stage 2 involves two additional regimens, Regimen C and Regimen D, and makes the comparison between Regimen B and Regimen C for the analysis of the primary endpoint. All treatment regimens are described in detail in the STREAM protocol, Section 2.1.3. Stage 1 and Stage 2 of the STREAM trial each have separate SAPs listed below. Each SAP has differences, but the fundamental statistical principles will be consistent across all SAPs.

Document	Description
Stage 1 SAP	All analyses relating to stage 1
Core Stage 2 SAP	Core analyses for stage 2
Extensive Stage 2 SAP	Expanded analyses for stage 2 supporting CSR

Compliance:

The trial will be conducted in accordance with the ethical principles that have their origin in the Declaration of Helsinki, in accordance with the principles of Good Clinical Practice (GCP) as laid down by the ICH topic E6 (Note for Guidance on GCP), and the applicable regulatory requirements in the participating countries.

Sponsor:

Vital Strategies, f/k/a The International Union Against Tuberculosis and Lung Disease, Inc. [name]

Tel (main): [contact] [contact]

Email: [contact]

Funders:

The United States Agency for International Development (USAID) UK Medical Research Council (MRC) / Department for International Development (DFID) Janssen Research & Development, LLP (Stage 2 only)

Main Contacts:

Co-Chief Investigator

[name] MRC Clinical Trials Unit at UCL Institute of Clinical Trials and Methodology [name]

[contact] [contact] Email: [contact]

Co-Chief Investigator

[name] MRC Clinical Trials Unit at UCL Institute of Clinical Trials and Methodology [name]

[contact] [contact] Email: [contact]

CONTENTS

1	Trial overview	8

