1.4 Study interventions

In Stage 2 of the STREAM trial, the primary comparison being made is between Regimen C and Regimen B, with secondary comparisons between Regimen D and Regimen B. In addition, a limited number of secondary analyses will make comparisons between Regimen A and the other regimens.

Regimen A: The locally-used MDR-TB regimen in accordance with 2011 WHO MDR-TB treatment guidelines¹.

Regimen B: Regimen B forms the control regimen for the primary and secondary comparisons, and is based on the regimen described by Van Deun 2010^2 (updated results³) consisting at the start of STREAM of clofazimine, ethambutol, moxifloxacin, and pyrazinamide given for 40 weeks, supplemented by isoniazid, kanamycin, and prothionamide for the first 16 weeks; this combination is referred to as Regimen B_{mox}. With Version 8.0 of the protocol Regimen B is modified by replacement of moxifloxacin with levofloxacin (referred to as Regimen B_{lev}). Regimen B without specification of which fluoroguinolone is in the regimen

refers to either (B_{mox} or B_{lev}). With Version 10.0 of the protocol, Regimen B is further modified to replace kanamycin with amikacin in sites where:

- the national TB program has replaced kanamycin with amikacin in line with revised WHO guidance⁴ and
- amikacin is available for the trial.

Kanamycin will continue to be used until the transition takes place within each country programme.

Regimen C: Regimen C is an all-oral modified version of Regimen B, consisting of bedaquiline, clofazimine, ethambutol, levofloxacin, and pyrazinamide given for 40 weeks, supplemented by isoniazid, and prothionamide for the first 16 weeks.

Regimen D: Regimen D a shortened modified version of Regimen B, consisting of bedaquiline, clofazimine, levofloxacin, and pyrazinamide given for 28 weeks, supplemented by isoniazid, and kanamycin for the first 8 weeks.

All patients in Stage 2 of the study will be followed up to Week 132. The primary analysis will be based on data accrued to Week 76; the data accrued to the date when the last patient is projected to have reached Week 96 will be used for the secondary long-term efficacy analysis; all data accrued to Week 132 will be used in the long-term safety analysis.

1.5 **Treatment phases**

Regimen B, Regimen C, and Regimen D each consist of 2 phases; an intense phase followed by a continuation phase, as shown in Figure 1.

[figure not shown]

Figure 1: Regimen treatment phases

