- 1. They are discontinued from their allocated study treatment and subsequently restarted on a different MDR-TB regimen.
- 2. Treatment is extended beyond the scheduled end of treatment for any reason other than making up days when no treatment was given (missed treatment) for a maximum of eight weeks. A maximum of 14 days of extra treatment (irrespective of reason) is acceptable before it is classified as treatment extension.
- 3. They are restarted on any MDR-TB treatment after the scheduled end of treatment, but before 76 weeks after randomisation.
- 4. They change their allocated study treatment for any reason other than the replacement of a single drug.
- 5. Bedaquiline is started where the allocated regimen did not originally contain that drug (Regimen A or B).
- 6. A second line injectable agent is started in Regimen C.
- 7. A drug from the class of nitroimidazoles (delamanid or pretomanid) or linezolid is started.
- 8. They die at any point during treatment or follow-up.
- 9. At least one of their last two culture results, from specimens taken on separate occasions, is positive.
- 10. They do not have a culture result within the Week 76 window.

Starting a single drug other than bedaquiline (in Regimen A or B) or from the class of nitroimidazoles (delamanid or pretomanid) or linezolid (in any regimen) is not considered to be a substantial change to the regimen and therefore does not result in an unfavourable outcome, providing none of the other criteria above are met.

An extension of the intensive phase of treatment in any study arm does not constitute an unfavourable outcome, as long as the extension is in accordance with the algorithms described in Figure 5 and Figure 6 in Section 1.5 for patients on Regimen B, Regimen C, and Regimen D. Similarly, the discontinuation of drugs that are not replaced does not constitute an unfavourable outcome.

These definitions of favourable and unfavourable apply to all four treatment regimens and for analyses of both the mITT, PP and mPP analysis populations.

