3.3 Primary outcome defined using estimands notation

We define 2 co-primary estimands that are the same in all components other than the handling of intercurrent events. Information on the estimator and estimation procedure are given in Section 6.

The estimands for the primary objective are defined as follows:

- (a) the comparison is between Regimen C and Regimen B as defined in Section 1.4;
- (b) the patient population of interest are patients with confirmed RR-TB that meet the inclusion/exclusion criteria as given in the trial protocol, Section 5 (see Section 4.4);
- (c) the endpoint is favourable outcome at Week 76 as defined in Section 3.2;

- (d) the population level summary is the difference in proportions of favourable outcome between treatment arms (See Section 6.1.1). Non-inferiority will be shown if the upper bound of the 2-sided 95% confidence interval of the difference in proportion of favourable outcomes at Week 76 between Regimens B and C is less than the 10% margin of non-inferiority;
- (e) the intercurrent events will be handled as described below.

Intercurrent Event	Strategy for Addressing Intercurrent Event for Primary Estimand 1	Strategy for Addressing Intercurrent Events for Primary Estimand 2
Change of 1 non-major drug in the allocated treatment regimen	Treatment policy strategy: use primary variable regardless of whether or not this intercurrent event had occurred	Treatment policy strategy: use primary variable regardless of whether or not this intercurrent event had occurred
Treatment extension to make up for days when no treatment was given (up to 8 weeks)	Treatment policy strategy: use primary variable regardless of whether or not this intercurrent event had occurred	Treatment policy strategy: use primary variable regardless of whether or not this intercurrent event had occurred
Other changes to allocated treatment regimen (drug substitutions, other treatment extensions, use of salvage regimens)	Composite strategy: occurrence of this intercurrent event is captured in the primary composite variable definition, a participant with this intercurrent event is considered unfavourable	Composite strategy: occurrence of this intercurrent event is captured in the primary composite variable definition, a participant with this intercurrent event is considered unfavourable

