6.2 Tabulation of primary endpoint classification

Since the primary endpoint is a composite of various components, the actual reason (component) for outcome will also be tabulated by treatment arm. Patients will be classified by the first event that made the patient unfavourable (see section 3.2) and further subclassified by whether their outcome is deemed to be bacteriologically related or not, based on a review of all data up to the time that the outcome occurred (see Section 6.2.1).

6.3 **Subgroup analyses**

This primary efficacy analysis will be repeated (in both mITT and PP analysis populations) in subgroups according to the following baseline characteristics:

- HIV infection status
- baseline drug resistance patterns (i.e. resistance to pyrazinamide and isoniazid)
- albumin levels (by severity grade)
- BMI (<16.0 kg/m², 16.0-18.4 kg/m², 18.5-24.9 kg/m², >25 kg/m²)
- cavitation (presence, absence)
- study centre/country
- age (<25, 25-<45, ≥45)

- sex
- Smoking history (current, ex, never)
- Smear grade
- Weight band (<33kg, 33-50kg, >50kg)
- Race.

6.4 **Sensitivity analyses**

The primary efficacy analysis will be repeated:

- A. Unadjusted for any covariates except randomisation protocol.
- B. Adjusted for randomisation stratification factors HIV status and centre. Small strata with fewer than 10 patients will be combined within geographical regions within country.
- C. Adjusted for randomisation stratification factors and any additional important covariate such as cavitation at baseline, baseline bacillary load or adherence.
- D. Ignoring substitutions of levofloxacin for moxifloxicin and vice versa when counting the number of drug substitutions within the definition of unfavourable outcome.
- E. Ignoring starting linezolid alone as a criterion for an unfavourable outcome.
- F. Reclassifying any participants with reinfection (based on genotype or DST) as "non-assessable" rather than unfavourable.
- G. Reclassifying any participants who died as a result of trauma (as adjudicated by independent review) as "non-assessable" rather than unfavourable.
- H. Reclassifying any participants with missing Week 76 culture results because of COVID-19 as "non-assessable" rather than unfavourable.
- Reclassifying any participants with missing Week 76 culture results because of COVID-19 as favourable if they meet the definition of favourable, with the latest of the 2 negative culture results being within the Week 68 window, unfavourable otherwise.

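### SAP 3.2 item 4 drops the protocol's exemption for kanamycin-to-amikacin changes, so the primary endpoint can be coded differently for some Regimen B patients

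*SAP*

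**What the plan says.** Protocol 11.2.1 (Unfavourable, item 4) tolerates the replacement of one drug. An asterisk on that phrase leads to a footnote: "Excluding changes from kanamycin to amikacin".

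SAP 3.2 (Unfavourable, item 4) repeats the rule with neither asterisk nor footnote: "They change their allocated study treatment for any reason other than the replacement of a single drug". The SAP's General Information says that "this Statistical Analysis Plan (SAP) supersedes the SAP as written in the protocol".

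Other places that bear on the point:

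- SAP 1.4 is the only place in the SAP that mentions amikacin. It describes the regimen: under protocol Version 10.0, "Regimen B is further modified to replace kanamycin with amikacin in sites where" two site-level conditions are met.
- SAP 3.3 defines the estimand by reference. Attribute (a): "the comparison is between Regimen C and Regimen B as defined in Section 1.4". Attribute (c): "the endpoint is favourable outcome at Week 76 as defined in Section 3.2".
- Protocol 7.2.2 says patients should receive the fluoroquinolone and "injectable allocated at randomisation unless there is a clinical or operational reason to make a change".
- SAP 6.4, sensitivity analysis D, exempts one like-for-like substitution, between the two fluoroquinolones: "Ignoring substitutions of levofloxacin for moxifloxicin and vice versa when counting the number of drug substitutions".

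**The concern.** Item 4 is part of the primary endpoint definition, and the two documents give different answers for one kind of patient: someone on Regimen B who moves from kanamycin to amikacin, has one other drug replaced, and is otherwise favourable. The protocol counts one replacement, which is tolerated. The SAP read literally counts two, which is unfavourable. Two programmers working from the SAP could code this patient differently and both defend the choice.

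The direction matters. Regimen C contains no injectable, so no Regimen C patient can be reclassified by this rule. In the primary comparison the literal reading can only lower the control arm's favourable rate, and that makes non-inferiority of C easier to show.

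**Working it through.** **Text comparison**

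| Regimen B patient, otherwise favourable | Protocol item 4 with footnote | SAP item 4 read literally |
|---|---|---|
| Injectable switch only | no counted replacement: not unfavourable | one replacement: not unfavourable |
| Injectable switch plus one other replacement | one counted replacement: not unfavourable | two replacements: unfavourable |

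Only the second row differs. A lone switch is safe in both documents. The non-major qualifier in the SAP 3.3 intercurrent-event table does not change that, because attribute (c) takes the endpoint from Section 3.2.

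**The plan's own sample size.** Inputs from SAP 2.1: 80% vs 82% favourable, margin 10 points, one-sided 2.5%, 80% power.

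n = (1.96 + 0.842)² × (0.80×0.20 + 0.82×0.18) / 0.12² = 7.849 × 0.3076 / 0.0144 = 167.7, so 168 per arm.

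The plan's 172 is within 3% of this and gives 81.0% power. 172 / 0.86 = 200 per arm, which matches the 400 total. These figures are not in dispute; they only supply the denominators below.

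**Effect per patient.** 1/172 = 0.58 points in the per-protocol (PP) population; 1/180 = 0.56 points if 180 are evaluable.

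**Illustration at the margin.** Assumptions: k = 1, 2 or 3 affected patients (the documents give no count); the protocol definition as the reference; true rates 80% for B and 70% for C.

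In one population, with s = k/n:

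- SE = √{[(0.8 − s)(0.2 + s) + 0.7×0.3] / n}, which is 0.0464 at n = 172 and s = 0
- chance of passing = Φ(−1.96 + s/SE)
- for k = 1 at n = 172: s = 0.0058, SE = 0.0466, s/SE = 0.125, Φ(−1.835) = 3.32%

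SAP 6.1.2 requires both mITT and PP to pass. I took PP as 172 per arm and mITT as 180 per arm. The 180 is the evaluable number in protocol 1.1.8; treating it as mITT is an assumption. With PP nested in mITT and the same true rates in both, the two test statistics have correlation √(172/180) = 0.978, and the joint probability is bivariate normal.

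| Affected patients k | PP alone (n = 172) | Both must pass, patients in both | Both must pass, patients in mITT only |
|---|---|---|---|
| 0 | 2.50% | 2.01% | 2.01% |
| 1 | 3.32% | 2.69% | 2.26% |
| 2 | 4.35% | 3.55% | 2.40% |
| 3 | 5.60% | 4.61% | 2.47% |

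A simulation of 2 million trials with Wald intervals agrees: 2.04% at k = 0; 2.70 / 3.49 / 4.49% with patients in both; 2.28 / 2.43 / 2.48% in mITT only.

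If mITT were 200 per arm (nobody excluded), the correlation is √(172/200) = 0.927. The joint figures with patients in both are then 1.63% at k = 0 and 2.19 / 2.90 / 3.79% for k = 1 / 2 / 3.

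**Can an affected patient be in PP?** Yes. SAP 4.4 keeps patients whose treatment was changed for an adverse event. Others stay only if the course was protocol-adherent, and SAP 4.4.1 counts a dose only when all study medications were taken correctly that day.

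**The case against.** The best counter-argument is that the SAP already contains the answer. Section 1.4 makes amikacin part of Regimen B at sites that have made the transition, and estimand attribute (a) defines the comparator by Section 1.4. On that reading a programme-driven switch is no change of allocated treatment, and the SAP agrees with the protocol. This is a fair reading, but it does not settle the matter. Section 1.4 describes what sites use and says nothing about counting a switch in mid-course. The protocol contains the same regimen description and its authors still added the footnote. Where the SAP wants a like-for-like substitution ignored, it says so, and analysis D covers only the fluoroquinolones.

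The second argument is that the affected group is tiny. The injectable is confined to an intensive phase of 16 weeks, 24 at most. Sites are told to keep the allocated injectable. Counting 96 weeks back from the end of November 2021 puts the last randomisation around late January 2020, so the period for mid-course switches was limited. Drugs stopped without replacement do not count. This stands: the group may be empty.

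The third is that the PP-alone percentages are not the trial's decision rule, the values of k are invented, and the mITT number is assumed. This also stands. Under the actual rule the chance exceeds 2.5% only if affected patients are also in PP, and with mITT at 200 per arm a single such patient is not enough (2.19%).

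**Conclusion.** The concern holds. The exemption is in the protocol and missing from the SAP, nothing else in the SAP supplies it, and the literal SAP rule classifies one kind of Regimen B patient differently on the primary endpoint. In the primary comparison any shift favours non-inferiority of C.

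The omission is certain from the text; a consequence for the result is not. If no patient has the switch plus one other replacement while otherwise favourable, the primary result is unchanged. If there are a few, the effect is about 0.6 points each on the control rate, limited by the requirement that both populations pass. This should be fixed because it touches the primary endpoint definition and costs little, not because the documents show that the conclusion is threatened.

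Two smaller inconsistencies in the same list do not carry the finding:

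- The protocol's item 4 clause for Regimen A changes caused by local guidelines is absent from the SAP. It bears only on the secondary Week 132 comparisons with A.
- Re-infection (protocol item 11) is missing from the SAP 3.2 list, although SAP 3.3 and sensitivity analysis F treat it as unfavourable.

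**What to change.** 1. Restore the protocol footnote in SAP 3.2 item 4, and align the wording on non-major drugs and drug substitutions in the SAP 3.3 table with it.
2. Count the Regimen B patients whose classification depends on the footnote: injectable switch, one other replacement, otherwise favourable. Start from patients whose reason in the SAP 6.2 tabulation is item 4. That tabulation records only the first qualifying event, so check each for a later unfavourable criterion.
3. State how these patients were coded and whether they are in PP.
4. Only if the count is above zero, report the primary mITT and PP results under both codings.
5. As consistency edits, restore the Regimen A guideline clause and add re-infection to the SAP 3.2 list.

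The cost is one line of endpoint wording, the small alignment edits and one count. Item 4 cannot be applied without drug-change data, so no new data collection should be needed. SAP 6.1.3 indicates that the Week 76 analysis has already been run, so a second version of the primary result is extra work only if the count is above zero.
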